Table 3.1 provides sample size calculations that use 27% as an estimate of the true favorable outcome rate in the IIT group. Sample sizes for alternative rates are also displayed. These were selected by using 23% (27%-2 times standard error) and 31% (27% + 2 times standard error) where the standard error is the standard error of the estimate from the DCCT study. Sample size calculations assume that an exact one sided test will be used and were calculated using the PASS (Hintze, 2011) sample size program. This table displays the sample sizes required for a one-sided 0.05 binomial test to achieve 80% and 90% power to detect true favorable outcome rates of 40%, 45%, 50%, 55%, and 60% in transplanted subjects compared to the selected rates in the IIT group. If the true favorable outcome rate at one year in IIT subjects is 27% then we would need to transplant 27 subjects to achieve 90% power to detect an improvement to 55% in transplanted subjects. We would need 19 subjects to achieve 80% power to detect 55% versus 27%. We

Statistical Analysis Plan

would need to transplant 40 subjects to ensure 90% power and 27 subjects to ensure 80% power if the true IIT rate is 31% and the true rate in islet transplant subjects is 55%.

Table 4.1: Sample sizes required to achieve 80% and 90% power

Rate in Transplanted Subjects	Power	Historic Rate - IIT		
		23%	27%	31%
40%	90%	64	113	246
	80%	46	84	175
45%	90%	39	64	105
	80%	31	46	76
50%	90%	28	39	59
	80%	21	30	43
55%	90%	21	27	40
	80%	15	19	27
60%	90%	15	19	27
	80%	12	16	17

We have chosen to transplant 24 subjects. This will provide approximately 90% power to detect a difference of 57% favorable outcome rate in islet transplanted subjects versus the estimated 27% favorable outcome rate in the DCCT population. Table 3.2 displays minimal detectable differences for sample sizes of 18, 24 and 30 subjects. With 24 subjects the smallest difference that can be detected with 90% power by a one-sided 5% level test is 57% compared to 27%. The minimal detectable difference is 52% compared to 27% with 80% power.

Statistical Analysis Plan

Table 4.2: Minimal detectable differences if the true IIT rate is 27%

	Power	
	90%	80%
18	62%	57%
24	57%	52%
30	53%	49%

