8.2 Analysis of binary outcome variables

Binary outcome variables will be displayed as percents with 95% exact confidence intervals (Rosner, 1995). The exact confidence interval (P_L, P_U) will be as the solutions to the following equations. If x is the observed outcome (that is, there are x successes in the 24 subjects) then the lower bound will be the solution P_L to the equation

$$0.025 = \Pr \{ \text{at least } x \text{ successes} \mid \text{probability of success} = p_L \} = \sum_{k=x}^{24} \binom{24}{k} p_L^k (1-p_L)^{24-k}.$$

The upper bound will be the solution to the equation

$$0.025 = \Pr \{ \text{no more than } x \text{ successes} \mid \text{probability of success} = p_U \} = \sum_{k=0}^x \binom{24}{x} p_U^k (1 - p_U)^{24-k}.$$

Standard search methods will be used to solve these equations.

8.3 *Analysis of time to event measures*

All time to event measures will be summarized using Kaplan-Meier (product limit) life table methods. Results will be displayed as survival plots. Tables with estimates and 95% confidence intervals for the rates at 1-year, 2-years, and 3-years after the first and last islet transplants will be provided. Separate analyses will be performed for time from first transplant and time from last transplant.

9. Analysis of Demographic and Baseline Measures

9.1 *Baseline Data*

Baseline data collected for the ITT analysis consists of demographic information and medical/physical assessments during the waiting period for islet transplant. These data will be grouped into the following categories:

- Demographic variables
 - Age
 - Sex
 - Race (White, Black, Hispanic, Asian and Other)
- Body Habitus and Quality of Life
 - Body Weight
 - Height
 - Body Mass Index (BMI)
- Diabetes Control
 - Insulin requirement (units/day)
 - HbA1c
 - Fasting and post prandial plasma glucose
 - Fasting and post prandial C-peptide
 - 90-minute C-peptide following consumption of Boost[®] or equivalent
 - 90-minute glucose following consumption of Boost[®] or equivalent
 - Number of severe hypoglycemic events in the last year
 - MAGE score
 - LI
 - Clarke Score
 - HYPO score
 - β -score
 - C-peptide/(glucose·creatinine) ratio

Statistical Analysis Plan

- Measures of Cardiovascular function
 - Carotid intimal thickness
 - Atherogenic profile (fasting lipids, c-reactive protein, serum amyloid A, Apolipoprotein A1, Apolipoprotein B, and the ratio of Apolipoprotein A1 and Apolipoprotein B).
- Measures of Renal function
 - Serum Creatinine

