12.3.4 Analysis for Hypoglycemia Fear Scale

Separate analyses of HFS will be computed for 75 ± 5 days after each transplant, and at one year, 2 years, and 3 years after the first and last transplants. We will calculate the sample mean and construct the 95% confidence interval of the mean DDS using the method for a continuous variable described in SAP section 9.2.2.

The longitudinal analyses will be repeated for the HFS.

12.4 *Analysis of Secondary Time to Event Outcomes*

Time to event outcomes include the following:

- Time to death (all cause and also cardiac related) and time to cardiovascular events (death, CVA, MI)
- Time to $HbA1c \leq 6.5\%$
- Time to first severe hypoglycemia episode
- Time to $HbA1c$ decreasing by at least 1%
- global treatment failure composite outcome measure defined as the time to the first occurrence of any of the following:
 - Death
 - Stroke
 - MI
 - Above the ankle amputation

All of the above will be ascertained from the SAE reports and will be adjudicated if an adjudication committee is available.

- Renal Failure (Any one of the following):
 - Initiation of dialysis; or
 - Renal transplantation
- Blindness: Visual acuity of 20/200 in both eyes.

Statistical Analysis Plan

- Poor diabetes control (if any of the following occur):
 - HbA1c > 9% and reduced less than 1% below the entry level, found 6 months or more following the first transplant and confirmed on repeat examination at least 30 days and no more than 60 days later. If confirmed, failure is the time of the initial draw;
 - Three consecutive monthly HbA1c values greater than the baseline value, with the first one being 6 months or more following the first transplant; or
 - Occurrence of two severe hypoglycemic events (requiring assistance from another person) within a three month period. Failure will occur at the time of the second hypoglycemic event.

The endpoints and the analyses in this protocol have adopted two principal time points for each transplanted subject: (1) the time of the first transplant and (2) the time of the last transplant. It is of interest to examine the time to events following each of these time points. The following analyses will be repeated using each of these milestones as time zero in the analysis. In the unlikely event that a subject has already reached an event at the time of the second transplant he/she will not be included in the analyses for that event for time from last transplant.

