All time to event outcomes will be summarized using Kaplan-Meier life table methods and survival plots. Estimates and 95% confidence intervals will be provided for rates at 1-year, 2-years, and three years after the first and after the last islet transplant. Confidence intervals will be computed as the estimate ± 1.96 standard errors of the product-limit estimates.

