14.2.1 Statistical Analyses of Adverse Events

AEs will be analyzed according to the body system described in the *CIT-TCAE* manual. Any event that appears in a body system will be categorized into one of the five severity grades according to the *CIT-TCAE* manual or the general definition of severity given in Table 7 and analyzed accordingly. For each event, we will analyze its incidence rate per 100 person-days. Suppose for each subject, the incidence of a particular event is a Poisson process with the homogeneous incidence rate λ . At the time of analysis, if a subject is only followed r days after the initiation of induction immunosuppression, the incidence of this event is distributed according to the Poisson distribution with mean $r\lambda/100$. The maximum likelihood estimate of the

Statistical Analysis Plan

incidence rate will be obtained based on data collected from the available subjects at the analysis time. The 95% confidence interval derived using the maximum likelihood estimator theory will be also reported. The results will be summarized in the table provided in SAP Appendix 4. Moreover, we will also list all the individuals who have ever had an incident of any of the AEs listed in Appendix 5 since their initiation of induction immunosuppression.

15. Interim Analyses and Safety Monitoring Analyses

The DSMB will be convened to review safety and efficacy data following National Institutes of Health (NIH) policy. When requested, formal interim analyses to assess safety and efficacy will be performed. Formal interim analyses will include distributions of endpoints, biomarkers and AEs. Additional analyses may be requested by the DSMB.

15.1 *Interim Analysis for Early Stopping*

We will use the method for interim analyses described by Emerson and Fleming (Emerson & Fleming, 1989) which is implemented in the SPlus module S+SeqTrial (TIBCO_Software, 2009) to provide cut-points for an interim analysis for futility. This module does not require specifying the timing of interim analyses and controls the overall type I and type II errors. In order to make what follows clearer we provide some notation. Let p represent the true probability of a favorable outcome in islet transplanted subjects.

The efficacy hypothesis is

$$H_{01} : p \leq 0.27 \text{ versus } H_{a1} : p > 0.27.$$

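### Kaplan-Meier limits fixed at estimate ± 1.96 SE break down for rare outcomes in 24 subjects, and the adverse-event rate interval should be replaced by an exact one

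*SAP*

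**What the plan says.** SAP section 12.4 forms each Kaplan-Meier interval by adding and subtracting 1.96 "standard errors of the product-limit estimates". It applies this at three horizons (one, two and three years) and from two time origins, the first transplant and the last. The outcomes covered include all-cause death, cardiac death, cardiovascular events, first severe hypoglycemia, two HbA1c milestones and a broad treatment-failure composite. Section 8.3 says "All time to event measures will be summarized using Kaplan-Meier (product limit) life table methods" and promises 95% intervals, but names no other interval, no transformation and no rule for zero events. The sample size is set in section 4: "We have chosen to transplant 24 subjects."

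For adverse events, section 14.2.1 assumes a homogeneous Poisson process for each event, with a rate per 100 person-days, and adds: "The 95% confidence interval derived using the maximum likelihood estimator theory will be also reported." Appendix 4 lays these rates out by body system, grade, event and relatedness, and labels the interval as based on MLE theory.

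Elsewhere the SAP uses exact limits: for binary outcomes (section 8.2), for the primary endpoint (section 10.1) and for immune sensitization (section 14.2).

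**The concern.** An untransformed Wald interval around a survival estimate depends on a standard error that shrinks to zero as the estimate approaches 100%. With 24 subjects, an outcome seen in none of them gets an interval with no width, and one seen in a few gets an upper limit that is not a possible survival probability. Cutting the upper limit off at 100% would tidy the table but would leave the lower limit too high.

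The stake is how safety is reported. The SAP introduction sets the trial's goal as showing that benefit is frequent enough to justify the risks of the procedure and the immunosuppression. Section 15.1 gives up stopping for efficacy so as to gather as much safety information as possible. A line reading survival 100% (100%, 100%) claims certainty that 24 subjects cannot provide.

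**Working it through.** **The plan's own figure.** For 24 subjects, section 4 gives about 90% power to detect 57% against 27% with a one-sided 5% exact test. Rejecting at 11 or more favorable outcomes gives an exact binomial type I error of 0.0369 and power of 0.904 at 57%. At 52% the power is 0.791, against a stated 80%. The figure reproduces, so n = 24 is used below. The SAP states no figure for the intervals themselves.

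**Kaplan-Meier limits.** Assume no censoring before the time point. With d events the estimate is S = 1 − d/24, and the Greenwood standard error is √(S(1−S)/24).

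- Planned limits: S ± 1.96 SE.
- Exact limits: Clopper-Pearson on 24 − d survivors of 24. At d = 0 the lower limit is 0.025^(1/24) = 0.858.
- Log-log limits: S raised to the power exp(±1.96 SE/(S·|ln S|)).

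For d = 1: S = 23/24 = 0.9583 and SE = √(0.9583 × 0.0417/24) = 0.0408. The planned limits are 0.9583 ± 0.0800, or 0.878 to 1.038.

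| Events | Planned | Exact | Log-log |
|---|---|---|---|
| 0 | 100% to 100% | 85.8% to 100% | undefined |
| 1 | 87.8% to 103.8% | 78.9% to 99.9% | 73.9% to 99.4% |
| 2 | 80.6% to 102.7% | 73.0% to 99.0% | 70.6% to 97.8% |
| 3 | 74.3% to 100.7% | 67.6% to 97.3% | 66.1% to 95.8% |
| 4 | 68.4% to 98.2% | 62.6% to 95.3% | 61.5% to 93.4% |

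The pattern mirrors at the other end: a lower limit below 0 at 21 to 23 events and zero width at 24. From 4 to 20 events the planned limits stay in range.

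**Coverage of the planned 95% interval**, summed over Binomial(24, S):

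| True survival | Coverage |
|---|---|
| 98% | 38% |
| 95% | 71% |
| 90% | 91% |
| 85% | 89% |
| 80% | 87% |
| 50% to 70% | about 94% |

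At 95% true survival the interval has zero width with probability 29% and runs above 100% with probability 68%.

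**Adverse-event rates, on the Wald reading.** With d events in T person-days the limits are (d ± 1.96√d) × 100/T. The lower limit is negative whenever 0 < d < 1.96² = 3.84, that is for 1 to 3 events, whatever T is. For illustration assume T = 24 × 365 = 8,760 person-days, or 87.6 units of 100 person-days. Rates are per 100 person-days:

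| Events | Wald | Exact Poisson |
|---|---|---|
| 0 | 0 to 0 | 0 to 0.0421 |
| 1 | −0.0110 to 0.0338 | 0.0003 to 0.0636 |
| 2 | −0.0088 to 0.0545 | 0.0028 to 0.0825 |
| 3 | −0.0045 to 0.0730 | 0.0071 to 0.1001 |
| 4 | 0.0009 to 0.0904 | 0.0124 to 0.1169 |

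The exact upper limit at 0 events is 3.689 expected events divided by T/100. For 24 subjects followed 75 days (T = 1,800) it is 3.689/18 = 0.205. For 1 year it is 3.689/87.6 = 0.042, and for 3 years (T = 26,280) 3.689/262.8 = 0.014. Coverage of the Wald interval is 39%, 63%, 86% and 80% at expected counts of 0.5, 1, 2 and 3.

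**The case against.** Four points can be made for the plan, and each limits what may be concluded.

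- **The adverse-event interval is not named as Wald.** A reader might infer that the adverse-event limits, as written, must collapse or go negative. The SAP does not support that. A profile-likelihood interval also rests on likelihood theory; at 0 events in 8,760 person-days it gives 0 to 1.921/87.6 = 0.022, and it never goes negative. A Wald interval on the log scale stays positive but is undefined at 0 events. The Wald reading is the ordinary one, but for this half the fault is conditional on it.
- **No event counts are given.** A reader might infer that most of the listed outcomes will have 0 to 3 events. That has no source in the SAP. Section 4 cites 70% reaching HbA1c ≤ 6.5% at one year, so that milestone is unlikely to be rare. The failure composite adds renal failure, blindness and poor diabetes control to the vascular events, and may not be rare either.
- **Exact limits elsewhere are not a contradiction.** Kaplan-Meier estimates allow for censoring and a simple proportion does not. Without censoring, however, 24 survivors of 24 would be reported as 85.8% to 100% under section 8.2 and 100% to 100% under section 12.4.
- **No decision hangs on these intervals.** Section 10.2 calls the secondary analyses descriptive. Section 15.2 takes suspension criteria from the protocol and does not tie them to these limits. Appendices 2, 3 and 5 show adverse-event counts and percentages, so a reader can see how few events lie behind a rate.

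These points narrow the concern. They do not rescue the Kaplan-Meier formula, which section 12.4 states without ambiguity.

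**Conclusion.** For rare time-to-event outcomes the Kaplan-Meier interval is wrong as written. In 24 uncensored subjects it has no width at 0 events, where data with no deaths remain compatible with mortality of up to 100 − 85.8 = 14.2%. At 1 to 3 events it passes 100%. Its coverage is about 38% and 71% at true survival of 98% and 95%, and about 91% at 90%.

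This rests on two assumptions: that outcomes such as death, cardiac death, stroke or infarction will have 0 to 3 events, and that there is no censoring before the time point. Outcomes with 4 to 20 events keep limits within range, although coverage can still fall somewhat short of 95%.

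For adverse-event rates the wording is under-specified. Its ordinary Wald reading fails at 0 to 3 events, so it is worth replacing, but the failure cannot be read off the text as certain. The primary analysis is exact and untouched. The matter concerns how secondary and safety results are reported.

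**What to change.** - **Section 12.4, with a matching line in section 8.3:** compute Kaplan-Meier limits on the complementary log-log scale. When no events have occurred by the time point, where log-log limits are undefined, report an exact binomial limit based on the number still at risk at that time. This is conservative under censoring: with 20 still at risk, for example, the lower limit is 0.025^(1/20) = 83.2% instead of 85.8%.
- **Section 14.2.1 and the Appendix 4 column heading:** replace the reference to likelihood theory with exact Poisson limits, including at zero events.

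The cost is a few sentences of SAP wording and standard software options. Data collection, sample size and the primary analysis do not change. The price is wider intervals for rare events, which reflects what 24 subjects can show.

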12.5 Sensitivity Analysis

Measurements of secondary endpoints may be missing at any time point. In our analysis report for the secondary endpoints, we will not impute missing values in the analysis but will report results for the observed data only. With close monitoring and data validation, the chance of having missing values will be minimized except that some serious adverse events (SAEs) may force subjects to withdraw from the study treatment or withdraw consent without a particular reason during the study. The interpretation of our analysis is strictly applied to the efficacy measurable population. However, a sensitivity analysis will be performed to determine the potential effect that missing values have on the analyses of the secondary endpoints.

Missing values due to SAE will be excluded from this analysis. The analysis on these subjects will be provided in SAP section 14.

We will conduct a sensitivity analysis assuming a missing at random mechanism: *i.e.*, we assume that a subject will withdraw consent at random with probability r . This probability will be estimated at each time point.

We will use the method of multiple imputation (Schafer, 1999) to develop estimates and standard errors that account for the missing data. We will compare the magnitude of the differences between multiple imputation estimates and observed data estimates to assess the potential affect

Statistical Analysis Plan

of the missing data. The assumption of missing at random cannot be verified and these results must be viewed with caution.

13. Other Exploratory Analyses

13.1 *Change from baseline*

For each secondary outcome and time point where it is appropriate, we will explore the change from baseline over time. The endpoints and time points are as follows:

- insulin requirements (measured quarterly years 1 and 2 post-first and post-last transplant then every 6 months until year 3 post-last transplant)
- HbA1c (measured at day 28 and then quarterly years 1, 2, and 3 post-first and post-last transplant)
- Clarke Score (measured at 6 months and year 1 post-first and post-last transplant then every 6 months until year 3 post-last transplant)
- β score (measured quarterly year 1 post-first transplant, quarterly years 1 and 2 post-last transplant then every 6 months until year 3 post-last transplant)
- Basal glucose (measured quarterly year 1 post-first transplant, quarterly years 1, 2, and 3 post-last transplant)
- 90-minute MMTT glucose (measured quarterly year 1 post-first transplant, quarterly years 1, 2, and 3 post-last transplant)
- Basal c-peptide (measured quarterly year 1 post-first transplant, quarterly years 1, 2, and 3 post-last transplant)
- 90-minute MMTT c-peptide (measured quarterly year 1 post-first transplant, quarterly years 1, 2, and 3 post-last transplant)
- C-peptide/(glucose*creatinine) ratio (measured monthly year 1 post-first transplant and post-last transplant, then quarterly post-last transplant)
- Serum creatinine (measured monthly year 1 post-first transplant and post-last transplant, then quarterly post-last transplant)
- Atherogenic profile (measured year 1 post-first transplant and yearly post-last transplant)
- Quality of Life measures (measured day 75, day 180, yearly post-first and post-last transplant)
- Carotid IMT (measured year 1 post-first transplant and yearly post-last transplant)

Data analyses will be based on change from baseline for each variable. Data analysis will use linear mixed models to describe the profiles of change across time while accounting for correlation within subjects. We will use two strategies. The first strategy will select specific time points where data are routinely measured (e.g. 1 year after first transplant, and 2 and 3 years after last transplant). Estimates of mean change from baseline at these specific time points and 95% confidence intervals will be reported. Contrasts will be used to compare mean changes among time points. We will use the method of Benjamini and Hochberg (Benjamini & Hochberg, 1995)

Statistical Analysis Plan

to account for the multiplicity of comparisons. Next, we will fit polynomial regression models to describe the profile of mean change with time. Data will be displayed graphically and parameter estimates and confidence intervals for regression parameters will be reported. We will use the multiple imputations method to determine the potential effect of missing data.

13.2 Comparison of time profiles of eligible subjects who are transplanted with eligible subjects who are not transplanted

For each secondary outcome and time point where it is appropriate, we will compare transplanted subjects to those subjects who remain on intensive insulin therapy (IIT) but do not receive a transplant. Subjects can remain on IIT for up to one year so the time points and comparisons will be determined by the measures that are obtained while subjects are on wait list. Prior to transplantation, measures are obtained when subjects satisfy the IIT entry criteria (baseline) and either quarterly or every six months while subjects are on the waitlist. The proposed endpoints and time points are as follows:

- insulin requirements (measured every six months)
- HbA1c (measured months 3, 6, 9, 11, 12 encompassing the IIT and WL periods)
- MAGE (measured every six months)
- LI (measured every six months)
- Clarke Score (measured every six months)
- Hypo Score (measured every six months)
- Quality of Life measures (measured quarterly while on wait list)

Analysis will use the linear mixed model approach to describe and test for differences across the time points between transplanted subjects post-transplant and non-transplanted subjects while they are on wait list. Time zero will be defined as the day that the IIT criteria was satisfied for those who do not get a transplant and as the day of transplant for those that are transplanted. Because the two populations will be different at baseline, the analyses will need to adjust for the baseline value of the same outcome as well as age, gender, and baseline BMI. We will use the linear mixed models approach for these analyses. We will use models which treat time as a categorical variable. We will use a standard “factorial” design with terms for time, treatment (transplant or no transplant), and the interaction between time and treatment. If the interaction is significant (which we expect) then we will test for the difference between treatments at each time point. We will report means and 95% confidence intervals for the difference at each time point. We will use the method of Benjamini and Hochberg (Benjamini & Hochberg, 1995) to account for the multiplicity of tests.

13.3 Comparison of pre-transplant and post-transplant time profiles of subjects who are transplanted.

For those who have been transplanted, we will compare the profiles of change over time while the subject was on waitlist to change over time after the subject has received a transplant. We begin collecting data pre-transplant when the subject becomes eligible for transplant. Time zero for the pre-transplant values will be when the subject becomes eligible for transplant. Time zero for post-transplant observations will be the day of transplant. The endpoints and times will be the same as those described in the previous section. Analysis will use the linear mixed model approach. The models will have terms for time, transplant status (pre-transplant or post-transplant), and the interaction between time and transplant status. If the interaction is significant (which we expect) then we will test for the pre-post difference at each time point. We will report means and 95% confidence intervals for the difference at each time point. We will use the method of Benjamini and Hochberg (Benjamini & Hochberg, 1995) to account for the multiplicity of tests.

14. Safety Analyses

Safety analyses will be conducted for the safety population. Summaries will be prepared for the targeted safety endpoints listed in the secondary endpoints and for all observed AEs organized by body system. The CIT consortium modified the National Cancer Institute (NCI) toxicity table to create a document relevant for trials of adult pancreatic islet transplantation. The resulting reference manual, “Terminology Criteria for Adverse Events (TCAE) In Trials of Adult Pancreatic Islet Transplantation,” provides descriptive terminology and a grading (severity) scale which will be utilized for adverse event (AE) reporting.

Regular safety analyses will be prepared for the Data Safety Monitoring Board (DSMB). These summaries will be used to monitor the overall safety profile of the study. These analyses will summarize all AE data that are available at the time of the DSMB meeting. Analyses will summarize AEs by MedDRA term and body system. Separate incidence summaries will be prepared for serious AEs, for nonserious AEs and for all AEs combined. Separate tables will summarize severity and attribution. Each AE can be attributed to the investigational agent (allogeneic islets), the immunosuppression, both or neither. Identical safety summaries will be included in the final statistical report.

The protocol also describes targeted safety endpoints. The planned analyses for general safety outcomes and for these targeted safety endpoints are described in the following few sections. While data summaries of variables describing renal failure and variables describing changes related to immunosuppression (immunosuppression and bone marrow suppression variables) are included in the SAP, no pre-planned analyses of these variables were described. Because of their extreme clinical importance, post-hoc analyses of these data tables will be reported in the clinical study report and labeled as post-hoc.

